10.5 Statistical Analyses

10.5.1 General Approach

The general approach to the statistical analysis will involve the use of Fisher's exact test, with corresponding 95% CIs, to present comparative outcomes between the two arms. A two-sample t- test will be used to analyze outcomes comparing mean changes in liver function and Kaplan-Meier estimates with a log rank analysis used for survival comparison. The descriptive statistics such as mean, median,

standard deviation and exact confidence interval for the primary endpoint (e.g., recruitment rate and screen failures) will be provided.

A planned interim analysis looking at feasibility will be performed at 6 months after the study is open to enrollment. A similar analysis will also be performed at 12 months. The purpose of these analyses will be to evaluate the endpoint for all subjects who have reached it, and to evaluate general recruitment rates to assess feasibility/futility.

10.5.2 Analysis of the Primary Endpoint(s)

The primary research question to be addressed is to measure feasibility in terms of recruitment rate and screen failures. Recruitment rate will be measured at 6 and 12 months and screen failures assessed by the detailed screen failure form at the time patients are approached for enrollment to ascertain specific reasons why patients may choose not to enroll. Of note, analysis of the screen fail forms will serve as an instructive tool for the investigators as to feasibility for a larger scale study. The granular data collected from the screen fail forms is not intended for publication.

10.5.3 Analysis of the Secondary Endpoint(s)

The secondary research questions to be addressed are as follows:

- 1. To compare the proportion of any toxicities (≥ grade 4) using CTCAE between RS and SBRT for patients with small (≤3 cm) solitary hepatocellular carcinoma (HCC).
 - The proportion of patients with toxicities will be provided along with corresponding 95% confidence intervals. Toxicity rates will be compared using a Fisher's Exact Test.
- 2. To compare the mean change in hepatobiliary function, as measured 3 months after treatment using a functional HIDA scan, between RS and SBRT for patients with small (≤3 cm) solitary hepatocellular carcinoma (HCC).
 - A two-sample t-test will be used to analyze mean changes in liver function as measured by functional HIDA scan.
- 3. To compare the mean change in patient-reported outcomes from baseline, at 3 and 6 months, between RS and SBRT, for patients with small (≤3 cm) solitary hepatocellular carcinoma (HCC), using FACT-G and COST FACIT.
 - A two-sample t-test will be used to analyze mean changes in patient reported outcomes as measured using FACT-G and COST FACIT.
- 4. To compare the disease-free survival (DFS) rates of RS and SBRT at 2 years using mRECIST on CT or MR for patients with small (≤3 cm) solitary hepatocellular carcinoma (HCC).
 - DFS rates will be compared using Kaplan-Meier estimates with a log rank analysis.
- 5. To compare time-to-secondary treatment (TTST) between RS and SBRT for patients with small (≤3 cm) solitary hepatocellular carcinoma (HCC) up to 2 years after initial treatment.
 - TTST rates will be compared using Kaplan-Meier estimates with a log rank analysis.

6. The proportion of patients with ORR at 6 months will be provided along with corresponding 95% confidence intervals. ORR rates will be compared using a Fisher's Exact Test.

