1.2 Schema

1.3 Schedule of Events

Procedures	Enrollment / Baseline	Pre-Treatment	Intervention /Treatment	1 month visit	3 month visit	6 month visit	9 month visit	12 month visit	15 month visit	18 month visit	21 month visit	24 month visit
		Within 30 days from enrollment	Within 45 days of pre- treatment visit procedures	30 days from end of treatment (+/- 15 days)	90 days from end of treatment (+/- 30 days)	180 days from end of treatment (+/- 30 days)	270 days from end of treatment (+/- 30 days)	360 days from end of treatment (+/- 30 days)	450 days from end of treatment (+/- 30 days)	540 days from end of treatment (+/- 30 days)	630 days from end of treatment (+/- 30 days)	720 days from end of treatment (+/- 30 days)
Informed consent	Х											
Demographics	Х											
Medical history	Х											
Randomization	Х											
Pregnancy Test (urine or serum) ^G	х											
Planning/mappin g arteriogram ^F		Х										
CT simulation ^E		Х										
Administer Study intervention ^c			х									
Physical exam	Х			Х	Х	х	х	х	х	х	х	х
Vital signs	Х			Х	Х	х	х	х	Х	х	х	х
Performance status	Х			Х	Х	Х	х	х	х	х	Х	х
Lab tests ^A	Х		Х	Х	Х	Х	х	х	х	х	х	Х
Adverse event review and evaluation ^H	Х	х	х	х	х	х						
Radiologic/Imagin g assessment ^D	Х				Х	Х	Х	х	х	х	х	х
Complete Case Report Forms (CRFs)	х		х	Х	Х	х	Х	х	х	х	Х	Х

Functional Hepatobiliary Scan		Хв		Х				
Patient Reported Outcome Measures (FACT- G, COST FACIT)	Х		Х	х	х			

A Complete Blood Count (CBC), Comprehensive Metabolic Profile (CMP), International normalized ratio (INR), and Alpha Fetoprotein (AFP). AFP will only continue to be drawn after baseline if initially elevated (>10 ng/mL)

B Baseline functional hepatobiliary scan should be completed after enrollment, but prior to start of treatment.

C SBRT Arm: Child Pugh A patients will receive a prescription dose of either 5000cGy in 5 fractions delivered every other day or 4800cGy in 3 fractions delivered twice weekly. Child Pugh B patients will receive a prescription dose of 4000cGy in 5 fractions delivered every other day. Patients will be seen at least once per week by a clinician to grade toxicities, with on-treatment labs (CBC, CMP, INR) each week. RS Arm: After planning arteriogram, subjects will return within 30 days to receive a single administration of Yttrium-90 into the segmental (≤2) artery supplying the tumor. Administered activity will be an amount prescribed to deliver a dose ≥200 Gy to the perfused tissue.

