8.0 STUDY EFFICACY AND SAFETY ASSESSMENTS

8.1 Efficacy Assessments

Patients will initially be flagged as potential candidates for the trial following a local tumor board discussion that the location and overall clinical picture would allow for either treatment as a viable option. Once tumor board agreement has been obtained, patients will be scheduled for a multi- disciplinary clinic visit where they will have a complete clinic visit with interventional radiology and radiation oncology back-

to-back. If after these visits patients fulfill inclusion/exclusion criteria, they will immediately thereafter be approached by a research coordinator and enrollment will be attempted.

If patients decline participation, a detailed screen fail form will be filled out to try and best ascertain reasons for declined participation. If the patient agrees to participate, they will be enrolled and randomized (as described above) at that time.

A virtual/telehealth provision will be permitted for all follow-up visits. Since the virtual visit does not allow for effective physical exam of all body systems and vitals are unable to be obtained virtually, these elements will not be required during virtual visits. Labs will be obtained, however, as well as required imaging. If questionnaires are required during a virtual/telehealth visit, they may be administered via REDCap survey.

Baseline: Labs, medical history/physical exam and PROs questionnaires will be obtained during the initial clinic visit prior to randomization. Subjects will be required to have an MRI or CT of the abdomen within 3 months of enrollment.

Pre-Treatment: Patients will return for functional hepatobiliary scan and treatment planning procedures prior to treatment (≤ 30 days from enrollment)

Treatment: Patients will undergo treatment as described above in Section 7.1.

Follow Up Visits:

One month (± 15 days) after treatment completion patients will return for a clinic visit with labs (CBC, CMP, INR, AFP (if elevated at baseline)), physical exam, and PROs using FACT-G and COSTFACIT.

Three months after treatment completion (± 30 days) patients will return for a clinic visit with labs (CBC, CMP, INR, AFP (if elevated at baseline)), physical exam, and PROs using FACT-G and COST FACIT. Patients will also undergo multi-phase contrast enhanced CT or MR of the abdomen and functional hepatobiliary scan.

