10.3 Sample Size Projections

The primary objective of the pilot study will be to access feasibility. 20 patients in total will be enrolled, with up to 10 patients per arm (depending on the amount of screen fails). These numbers should be sufficient for the assessment of feasibility.

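### Low priority: changes in HIDA, FACT-G and COST FACIT are compared by unadjusted t-tests although a baseline is collected; ANCOVA may add some precision. Separately, the PRO time points disagree on month 1

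*Combined protocol and SAP*

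**What the plan says.** **Analysis method.** Section 10.5.1 says that a two-sample t-test "will be used to analyze outcomes comparing mean changes in liver function and Kaplan-Meier estimates". Section 10.5.3 item 2 repeats this for HIDA: "A two-sample t-test will be used to analyze mean changes in liver function as measured by functional HIDA scan". Item 3 covers the questionnaires: "A two-sample t-test will be used to analyze mean changes in patient reported outcomes as measured using FACT-G and COST FACIT". No section adds the baseline value to the comparison.

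**Baselines.** All three are scheduled. Note B to the Schedule of Events (1.3) says: "Baseline functional hepatobiliary scan should be completed after enrollment, but prior to start of treatment". Section 8.1 says that "PROs questionnaires will be obtained during the initial clinic visit prior to randomization". The PRO baseline therefore precedes randomisation. Patients are randomised at enrolment, so the HIDA baseline follows randomisation but still precedes treatment.

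**Sample size.** Section 10.3 plans 20 patients, up to 10 per arm, and justifies this by feasibility alone: "These numbers should be sufficient for the assessment of feasibility". It gives no SD, correlation, effect size or power.

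**PRO time points.** Section 10.5.3 item 3 restates the objective as "To compare the mean change in patient-reported outcomes from baseline, at 3 and 6 months, between RS and SBRT". The endpoint and objective lines of 10.2.2 item 3 also give 3 and 6 months. The null and alternative hypotheses in that same item give 1, 3 and 6 months, as do the synopsis, section 4.2 and Table 1. The one-month visit in 8.1 includes "physical exam, and PROs using FACT-G and COSTFACIT".

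**The concern.** Subtracting the baseline fixes its coefficient at 1. When the within-arm slope of follow-up on baseline is not 1, the change score carries avoidable variance, and a chance imbalance in baseline between two arms of 10 moves the estimated difference. ANCOVA estimates the slope instead, from data that the trial already collects.

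Little is at stake. No decision rule uses these secondary endpoints and none is powered. With about 10 per arm, however, the estimated difference and its interval are nearly all they can contribute, so a cheap gain in precision is worth considering.

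The month-1 discrepancy is a separate matter. It leaves unclear whether two comparisons (one per instrument) that the hypotheses in 10.2.2 include will be reported.

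**Working it through.** **Inputs.** From the documents: 20 patients, up to 10 per arm (10.3); 10% unanalyzable accruals (9.0), so 20 × 0.9 = 18, or 9 per arm, as a lower case. The 95% level is taken from the intervals in 10.5.1. Assumed, because the documents give neither: rho, and k = follow-up SD / baseline SD. The plan has no figure of its own to reproduce here.

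**Variances, in units of the baseline variance.**
- Change score: 1 + k² − 2·rho·k
- ANCOVA residual: k²(1 − rho²)
- Difference: (1 − rho·k)², which is never negative. ANCOVA's residual variance is never the larger, and the two are equal only when the within-arm slope rho·k is 1.

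**Cost of estimating the slope, N = 20.** One degree of freedom: t goes from 2.101 (18 df) to 2.110 (17 df), a ratio of 1.0042. Expected variance inflation is 1 + 1/(N − 4) = 1.0625.

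**Worked case, k = 1, rho = 0.5.** Change-score variance 1 + 1 − 1 = 1; residual variance 0.75. Approximate width ratio √(0.75 × 1.0625) × 1.0042 = 0.896; simulation gives 0.895. The mean t-test half-width is 2.101 × 0.986 × √0.2 = 0.927 baseline SDs, where 0.986 is the expected value of the sample SD on 18 df relative to the true SD. With ANCOVA it is 0.927 × 0.895 = 0.83.

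**Simulation, 10 per arm.** 200,000 trials per cell, bivariate normal, same SDs and slope in both arms. Each cell gives the ratio of mean 95% CI widths (ANCOVA / t-test) and, in brackets, the share of single trials in which ANCOVA is narrower (good to about one percentage point).

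| k | rho 0.3 | rho 0.5 | rho 0.7 | rho 0.8 |
|---|---|---|---|---|
| 0.8 | 0.732 (97%) | 0.781 (95%) | 0.818 (92%) | 0.827 (91%) |
| 1.0 | 0.833 (90%) | 0.895 (80%) | 0.952 (62%) | 0.980 (51%) |
| 1.2 | 0.902 (78%) | 0.965 (58%) | 1.016 (31%) | 1.032 (21%) |
| 1.3 | 0.927 (71%) | 0.987 (48%) | 1.029 (23%) | 1.032 (21%) |
| 1.5 | 0.964 (58%) | 1.015 (32%) | 1.032 (20%) | 1.009 (36%) |

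At k = 1 the break-even rho is 0.87 at 10 per arm and 0.85 at 9. Coverage is 0.949 to 0.951 for both methods in every cell.

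**Worst case, slope exactly 1.** The mean width ratio is 1.033 at 10 per arm, 1.038 at 9 and about 1.045 at 8. On the variance scale the loss is 6.25% at 10 per arm and 7.1% at 9. These are averages: at 10 per arm, 5% of single trials have an ANCOVA interval about 13% or more wider than the t-test interval.

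**PRO time points.** The hypotheses in 10.2.2 item 3 imply 2 instruments × 3 visits = 6 comparisons. The objective in 10.5.3 item 3 names 2 × 2 = 4. The t-test sentence there names no visit, so it does not settle the matter.

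**The case against.** The strongest reply is that this is a choice between two valid analyses. The t-test on mean change answers the hypotheses exactly as 10.2.2 states them, and the benefit of ANCOVA rests on quantities that the documents do not give. That stands. Nothing in the plan says which rho or k is realistic, and for k of 1.2 or more the table has cells where ANCOVA loses on average and in most single trials. The 3–4% limit is a mean and does not bound what happens in the one trial that will be run.

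Three stronger readings are tempting, and the documents support none of them:

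- *That the t-test is biased or invalid.* Its coverage is nominal, as is ANCOVA's. Section 10.4 removes and replaces RS patients found ineligible at the planning arteriogram, so the analysed groups are not strictly those randomised. That affects both methods alike, and baseline adjustment does not cure it. The post-randomisation HIDA baseline likewise enters both methods.
- *That ANCOVA will give the narrower interval in this trial.* With equal SDs and rho 0.8 it does so only about half the time.
- *That month-1 PROs are not collected or have been dropped.* Sections 1.3 and 8.1 schedule them; only some of the wording omits them.

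What survives the reply is that the baseline is already collected, the mean cost is small, and the mean gain is appreciable if rho is low to moderate and the SDs are similar.

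**Conclusion.** The point holds as a low-priority improvement in precision. It does not put the validity of the planned comparison in doubt. With k = 1 and 10 per arm, the mean interval is about 17% narrower at rho 0.3, falling to 2% at rho 0.8. With a larger follow-up SD and moderate to high rho it is up to 3.3% wider on average, and more than that in some single trials. The figures assume normal data, a common slope and common SDs across arms, and 8 to 10 analysable patients per arm; rho and k are assumptions throughout. Since no decision depends on these endpoints, the authors could reasonably keep the t-test. The month-1 discrepancy needs no assumption: it is a genuine but minor inconsistency and adds no weight to the first point.

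**What to change.** 1. In 10.5.1 and 10.5.3 items 2 and 3, replace the two-sample t-test by ANCOVA of change on arm plus the baseline value of the same measure. Keeping change as the outcome leaves the endpoints and hypotheses as written; using the follow-up value instead gives the same arm difference. Settle this before outcomes are compared by arm.
2. Report the adjusted RS−SBRT difference with a 95% CI for HIDA at 3 months, and for FACT-G and COST FACIT separately at each PRO visit. For comparisons between arms, the plan at present ties 95% CIs to the Fisher's exact analyses and does not mention them for mean change.
3. Separately, reconcile the PRO time points: bring the endpoint and objective lines of 10.2.2 item 3 and the objective in 10.5.3 item 3 into line with the 1, 3 and 6 months given in the synopsis, 4.2, Table 1, the 10.2.2 hypotheses and the visit schedule.

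The cost is wording, one degree of freedom per model, and the possible widening set out above. No extra data or visits are needed.

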2.2 Background

Primary surgical resection remains the first-line treatment for small HCC (<3 cm) in patients with preserved liver function. Child-Pugh class A patients with small HCC have shown a 5-year overall survival rate around 70% following surgical resection. Unfortunately, many patients are not eligible for surgical resection either secondary to tumor location, underlying portal hypertension or co-morbidities. The NCCN guidelines recommend surgical resection when possible, with locoregional therapy being recommended for patients who are not candidates for resection (recommending ablation, arterial directed therapies, and external beam radiation therapy as category 2B recommendations).

There are no data directly comparing stereotactic body radiotherapy (SBRT) to high-dose segmental radioembolization (radiation segmentectomy). Both of these treatment approaches have relatively small published data sets demonstrating efficacy and relative safety, but a head-to-head comparison has yet to be performed. In addition to efficacy and toxicity, patient-reported outcomes (PROs) such as quality of life (QoL) and patient out-of-pocket cost of care should play a role in the choice of treatment of these patients. The majority of patients with HCC have chronic liver disease which may already affect their QoL. Many patients, particularly at our institution, also travel multiple hours for their treatments and the difference between the number of visits required for radioembolization and SBRT may affect their treatment choice and PROs.

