4.2 Secondary Objectives (SO)/ Secondary Endpoints (SE)

- SO: To compare the proportion of patients with toxicities (≥ grade 4) using CTCAE version 5.0 between RS and SBRT for patients with small (≤3 cm) solitary hepatocellular carcinoma (HCC). Only those toxicities at least possibly related to treatment will be considered.
 - **SE:** Laboratory (CBC, CMP, INR)/clinical toxicities measured using CTCAE version 5.0 up to 6 months post treatment.
- 2. **SO**: To compare the mean change in hepatobiliary function, as measured 3 months after treatment using a functional HIDA scan, between RS and SBRT for patients with small (≤3 cm) solitary hepatocellular carcinoma (HCC). SE: Change in % radiotracer extraction from baseline, on functional HIDA scan, 3 months after treatment
- 3. **SO:** To compare the mean change in patient-reported outcomes (PROs) from baseline, at 1, 3 and 6 months, between RS and SBRT, for patients with small (≤3 cm) solitary hepatocellular carcinoma (HCC), using FACT -G and COST FACIT questionnaires. **SE:** Change in FACT-G and COST FACIT from baseline at 1, 3 and 6 months
- 4. SO: To compare the disease-free survival (DFS) rates of RS and SBRT at 2 years using mRECIST on CT or MR for patients with small (≤3 cm) solitary hepatocellular carcinoma (HCC).SE: DFS at 2 years after treatment completion as measured with mRECIST on CT or MR
- 5. **SO:** To compare time-to-secondary treatment (TTST) between RS and SBRT for patients with small (≤3 cm) solitary hepatocellular carcinoma (HCC) up to 2 years after initial treatment. SE: TTST for target tumor up to 2 years following treatment.

6. **SO:** To measure the objective response rate (ORR) of radiation segmentectomy (RS) and stereotactic body radiation therapy (SBRT) as measured at 6 months using mRECIST (appendix IV) for patients with small (≤3 cm) solitary hepatocellular carcinoma (HCC) to better allow for an appropriately powered trial evaluating the efficacy of these treatments. **SE:** ORR at 6 months after completion of treatment using mRECIST on multiphase CT or MR.

Table 1: Justification for Endpoints

	OBJECTIVES	ENDPOINTS	JUSTIFCATION FOR ENDPOINTS		
Pri	mary				

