1.	To assess feasibility as measured by screen failures and rate of recruitment into a randomized trial comparing RS and SBRT	 a. Recruitment rates measured at 6 and 12 months b. Screen failure form 	 a. Given the technical differences between the two modalities, recruitment may prove difficult so analyzing recruitment rates at 6 and 12 months may reveal futility. b. Screen failure form will help PI assess feasibility for a larger scale study. 		
Sec	ondary				
1.	To compare the proportion of toxicities (≥ grade 4) using CTCAE between RS and SBRT for patients with small (≤3 cm) solitary hepatocellular carcinoma (HCC).	Laboratory (CBC, CMP, INR)/clinical toxicities measured using CTCAE	Provide a measure of each treatment's potentially deleterious effect on the surrounding liver parenchyma.		
2.	To compare the change in hepatobiliary function, as measured 3 months after treatment using a functional HIDA scan, between RS and SBRT for patients with small (≤3 cm) solitary hepatocellular carcinoma (HCC).	Change in % radiotracer extraction from baseline, on functional HIDA scan, 3 months after treatment	Provide a measure of each treatment's potentially deleterious effect on the surrounding liver parenchyma.		
3.	To compare the change in patients reported outcomes from baseline, at 1, 3 and 6 months, between RS and SBRT, for patients with small (≤3 cm) solitary hepatocellular carcinoma (HCC), using FACT-G and COST FACIT.	Change in FACT-G and COST FACIT from baseline at 1, 3 and 6 months	Provide insight into whether or not one treatment is more deleterious to a patient's quality of life overall, as measured by the patient themselves.		

4.	To compare the disease- free survival (DFS) rates of RS and SBRT at 2 years using mRECIST on CT or MR for patients with small (≤3 cm)	DFS at 2 years after treatment completion as measured with mRECIST on CT or MR	DFS at 2 years will allow for assessment of both target and non-target recurrence in this population who are often prone to have new tumors secondary to cirrhosis.
5.	To compare time-to- secondary treatment (TTST) between RS and SBRT for patients with small (≤3 cm) solitary hepatocellular carcinoma (HCC) up to 2 years after initial treatment.	TTST for target tumor up to 2 years following treatment.	TTST will allow for some measure of the long term efficacy of the treatment as these tumors are often treated multiple times.

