Six months after treatment completion (± 30 days) patients will return for a clinic visit with labs (CBC, CMP, INR, AFP (if elevated at baseline)), physical exam, and PROs using COST FACIT and FACT-G. Patients will also undergo multi-phase contrast enhanced CT or MR of the abdomen and ORR will be measured by two separate abdominal radiologists, using mRECIST, who will have been blinded to the treatment received.

9-24 months: Patients will continue to be followed every three months in clinic with labs, physical exam, and imaging per standard of care. Further intervention will be performed (if needed) as standard of care and DFS and TTST will be recorded up to 2 years from the completion of treatment.

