9.0 PARTICIPANT DISCONTINUATION/WITHDRAWAL

Participants may withdraw voluntarily from the study, the PI may discontinue a participant from the study, or patients may be lost to follow-up. The overall estimation of total unanalyzable accruals is 10%.

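### The TTST analysis does not say how death before retreatment is handled, and a Kaplan-Meier rate with deaths censored can overstate the 2-year probability of retreatment

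*Combined protocol and SAP*

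**What the plan says.** Section 4.2 gives the endpoint as "TTST for target tumor up to 2 years following treatment", and section 10.2.2 repeats it. Death is not named as part of the event. Table 1 gives the purpose: "TTST will allow for some measure of the long term efficacy of the treatment as these tumors are often treated multiple times". Section 8.1 sets the horizon: "DFS and TTST will be recorded up to 2 years from the completion of treatment".

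The analysis is one sentence in section 10.5.3: "TTST rates will be compared using Kaplan-Meier estimates with a log rank analysis". The general approach in section 10.5.1 adds nothing specific to TTST; it names "Kaplan-Meier estimates with a log rank analysis used for survival comparison".

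No section gives a censoring rule for TTST, a composite definition that includes death, or a competing-risk method. Section 9.3 defines loss to follow-up by missed visits and failed contact and does not address death. Section 10.3 sets the size: "20 patients in total will be enrolled, with up to 10 patients per arm".

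**The concern.** A patient who dies without retreatment of the target tumour can no longer have the TTST event. If that death is censored, Kaplan-Meier removes the patient from the risk set and in effect assigns them the same later retreatment hazard as those still alive. The complement of the curve, 1-KM, then describes a setting in which nobody dies. It is not the proportion of treated patients who will be retreated by 2 years.

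The plan refers to TTST rates, so a 2-year percentage per arm will probably be read off the curve. That percentage may be taken as the chance of needing further treatment, and it may be carried into planning of a larger trial. Because the handling of death is not stated, the analyst would also have to settle it after the data are in.

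**Working it through.** The plan states no TTST rate, event count or power, so there is no figure of its own to reproduce. The check compares the planned estimate with the cumulative incidence.

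**Inputs**
- Horizon T = 2 years (section 8.1).
- Up to 10 patients per arm (section 10.3).
- Mortality: the documents give none for this population. Section 2.2 cites a "5-year overall survival rate around 70% following surgical resection" in Child-Pugh A patients with small HCC. It is used here only as an anchor. The values 25%, 30% and 40% dead by 2 years are assumptions.
- Retreatment: no rate is given. A 2-year 1-KM of 30% is assumed, with 20% and 40% as a range.
- Hazards are taken as constant and independent.

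**Step 1. Deaths by 2 years from the anchor**

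1 - 0.70^(2/5) = 0.133, or about 1.3 patients in an arm of 10.

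**Step 2. Cumulative incidence behind a given 1-KM**

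With retreatment hazard r and death hazard d:
- 1-KM (deaths censored) = 1 - exp(-rT)
- cumulative incidence = r/(r+d) × [1 - exp(-(r+d)T)]

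For 1-KM = 0.30, r = -ln(0.70)/2 = 0.1783. With 13.3% dead, d = -ln(0.867)/2 = 0.0713. The cumulative incidence is 0.1783/0.2497 × (1 - 0.70 × 0.867) = 0.714 × 0.393 = 0.281.

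| 2-year deaths | 1-KM | Cumulative incidence | Excess (points) |
|---|---|---|---|
| 13.3% (anchor) | 30% | 28.1% | 1.9 |
| 25% (assumed) | 30% | 26.3% | 3.7 |
| 40% (assumed) | 30% | 23.8% | 6.2 |

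At 13.3% deaths, a 1-KM of 20% corresponds to 18.7% and a 1-KM of 40% to 37.5%. The relative excess is about 7%.

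**Step 3. The other reading**

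If death is counted as an event, the curve at 30% and 13.3% gives 1 - 0.70 × 0.867 = 39.3%. That is the probability of retreatment or death, against a retreatment probability of 28.1%.

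**Step 4. One arm of 10 with 3 retreatments (crude 30%)**
- One death before all three: 1 - (8/9)(7/8)(6/7) = 33.3%.
- Two deaths before all three: 1 - (7/8)(6/7)(5/6) = 37.5%.
- All deaths after the last retreatment: 1 - (9/10)(8/9)(7/8) = 30.0%, so no excess.

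**Step 5. Sampling error**

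In 20,000 simulated arms of 10, mean 1-KM was 29.9% against a mean cumulative incidence of 28.0% with 13.3% deaths, and 29.9% against 25.4% with 30% deaths. The standard deviation of the estimates was about 14 to 16 points.

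**The case against.** Four points can be made for the plan.

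1. It never says that deaths are censored. This stands: censoring is inferred from the named method and the endpoint, and the documented defect is silence. The silence does not remove the problem, because step 3 shows that the other common choice does not give a retreatment probability either.

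2. The hypotheses in section 10.2.2 concern equality of TTST between arms, and the log-rank test with deaths censored is a valid comparison of cause-specific retreatment hazards. This stands. A reader might infer that the planned arm comparison is distorted, or that the log-rank test should be replaced by a test on cumulative incidence. The documents do not support either inference, because they do not name cumulative incidence as the target. For a measure of treatment efficacy, the retreatment hazard among living patients is a defensible target. A test on cumulative incidence has its own cost: with equal retreatment hazards (1-KM 30% in both arms) and 10% against 30% deaths, cumulative incidence is 28.6% against 25.5%, so the arm with more deaths looks better.

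3. The excess is not inevitable. It is zero if no death precedes a later retreatment. At 13.3% mortality an arm of 10 has no deaths by 2 years with probability 0.867^10, about 24%.

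4. The anchor comes from resected Child-Pugh A patients, while section 5.1 admits Child-Pugh scores up to 7. This stands, and it is why a range is shown. TTST is also secondary in a 20-patient feasibility study, and Table 1 names ORR as the endpoint that may inform the later sample size.

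**Conclusion.** The point holds as a minor improvement to the descriptive estimate. The plan leaves death before retreatment unaddressed, and its only named estimator does not give the 2-year probability of retreatment under either usual handling of death.

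At a 1-KM of 30%, the excess with deaths censored is about 2 points on the only documented anchor and about 4 to 6 points at an assumed 25% to 40% mortality. These figures rest on constant, independent hazards and on an assumed retreatment rate. They are well below the sampling standard deviation of one arm. A reader might infer that the rate is biased upward in both arms in every case. That goes too far, because the excess depends on a death preceding a later retreatment. Neither the feasibility objective nor the log-rank test is affected.

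**What to change.** In section 10.5.3:
- Define the TTST event as the first secondary treatment of the target tumour, and state that death before it is a competing event.
- Report the 2-year TTST rate by arm as Aalen-Johansen cumulative incidence with a 95% CI, alongside the number of deaths without retreatment.
- Keep the log-rank test, labelled as a comparison of cause-specific retreatment hazards.

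The cost is a short addition to the SAP and standard software, with no change to accrual or visits; the analysis needs dates of death through 2 years. There are two downsides. The curve is less familiar, and cumulative incidence can look lower in an arm with more deaths, so it must be read with the death counts beside it.
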